The proposed study aims to evaluate the efficacy of a single intramuscular (IM) dose of gentamicin in the treatment of pharyngeal gonorrhea. Secondary objectives include documenting the efficacy stratified by minimal inhibitory concentration (MIC) compared with the gentamicin peak level in order to estimate a pharmacodynamic criterion. We will also attempt to determine whether gentamicin monotherapy induces antimicrobial resistance among treatment failures. Lastly, we will evaluate the tolerability of 360 mg of IM gentamicin, stratified by subject weight (i.e. weight based dosing). The specific aims are:

- 1) Determine the proportion of persons whose pharyngeal gonococcal infections are cured with a single dose of 360mg gentamicin intramuscularly alone.
- 2) Evaluate the *renal safety* and tolerability of 360mg IM of gentamicin.
- 3) Document mean peak gentamicin levels following 360mg IM of gentamicin stratified by weight.
- 4) Estimate the best pharmacodynamics criterion (i.e. peak/MIC ratio) for pharyngeal gonorrhea treated with gentamicin using individual and mean peak gentamicin levels and NG isolate MIC.
- 5) Among treatment failures, conduct exploratory analyses comparing pre- and post-treatment MIC for evidence of induced resistance.

Study Design: Prospective cohort

Study Population & Inclusion Criteria:

Persons diagnosed with pharyngeal gonorrhea who are not yet treated

Exclusion criteria:

- Age less than 16 years
- Receipt of antibiotics in ≤ 30 days
- Known allergy to any aminoglycoside
- History of renal disease (including diagnosis of solitary kidney, chronic renal insufficiency, renal cell carcinoma etc),
- Use of concurrent nephrotoxic drugs or muscle relaxants
- History of diabetes
- History of hearing loss or tinnitus
- Concurrent infection with syphilis or chlamydia
- Pregnancy and/or nursing
- Unable to return for a follow-up visit 4-7 days (+/- 1 day).
- Study team's discretion

Intervention: 360mg IM gentamicin x 1

Primary Outcome: Negative gonorrhea culture 4-7 days (+/- 1 day) after treatment

Sample Size: 60 persons

Statistical Analysis Plan:

[figure not shown]

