The primary endpoint is the pharyngeal cure rate – that is, the proportion of subjects who return for TOC who clear their infections as evidenced by a negative culture 4-7 (+/-1) days after treatment. Persons who test negative for NG at their enrollment visit (i.e. infection cleared between initial clinical screening test and enrollment) will be excluded from analysis. Treatment failure will be defined as a positive culture 4-7 (+/-1) days after treatment. The cure rate will be calculated as the number of cured subjects divided by the total number of subjects who received treatment and returned for follow-up testing in a modified an intention to treat (mITT) analysis. We will also calculate the 95% CI for this proportion.

We will conduct an interim analysis after we have primary outcome results for 25 subjects. If the cure rate is $\leq 44\%$ (99% CI 17% – 74%; i.e. 12 persons of 25 persons with a positive culture on treatment date fail treatment), we will stop the study. We will also monitor for renal toxicity at the interim analysis. We plan to obtain pre-treatment and post-treatment Creatinine. Increases $>40\%$ will be considered significant. If more than 20% of the study population has a $>40\%$ increase in serum Creatinine, we will halt the study. We chose 20% because if 20% of subjects experience renal toxicity it is unlikely to be due to chance (95% CI 7 – 40%). For our second objective, we will compare the MIC of cures to treatment failures using a stratified approach (Table 2), and we will correlate this data with individual peak gentamicin level in order to estimate the ideal pharmacodynamic (PD) criterion (Obj. 2). For persons who fail treatment we will also compare the pre- and post-treatment genatmicin MIC to estimate whether single dose gentamicin therapy can “induce” resistance (Obj. 3) as an exploratory analysis. We will consider an increase in the MIC by two doubling-dilutions (i.e. from MIC of 2 to 8 $\mu\text{g/mL}$, or 8 to 32 $\mu\text{g/mL}$) to represent induced resistance, and we will calculate the

proportion of isolates among those that fail treatment that demonstrate induced resistance following receipt of gentamicin. Lastly, we will report the number and proportion of subjects who report side effects.

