The study coordinator or clinician will fill out the first section of the data entry form (see Appendix E) which includes subject contact information, demographic information (include sex assigned at birth, current gender identity, sexual orientation, race/ethnicity), HIV status, anatomic sites of infection, height, weight, concurrent medications and medical history.

2. Diagnostics and Baseline Clinical Data:

The study clinician will obtain specimens for culture from all anatomic sites that were screen positive for gonorrhea. This will include the pharynx (by inclusion criteria) and possibly the rectum, urethra and endocervix, per routine clinical care. A pharyngeal specimen is taken by gently touching a swab to the posterior aspect of the throat and moving it up and down, and over the tonsils for 5-10 seconds. Rectal swabs involved inserting a small q-tip like swab in the rectum approximately 3 cm and twirling it around approximately five times. To obtain a urethral swabs, clinician use a smaller swab and insert it approximately 0.5 – 1 cm into the urethra and twirl 1-2 times. Endocervical specimen collection requires a pelvic exam with speculum. Once the cervical os is visualized the clinician inserts the swab into the cervical os approximately 1 cm and spins it about 5 times for an adequate sample. Swabs for culture will be plated directly onto Thayer-Martin media and placed in a candle (CO₂) jar. Plates will be transported to the PHSKC lab daily, those that grow *N. gonorrhoeae* will be sent to the Neisseria Reference Laboratory (NRL) for antimicrobial susceptibility testing. The procedures described above are all part of routine clinical care.

The study clinician will also obtain blood to check a baseline creatinine to measure renal toxicity. This blood draw will occur with the PK blood draw 30, 45, or 60 minutes after dosing to avoid obtaining blood from the subject more than once.

3. *Treatment:*

Once all diagnostic procedures have been completed, the study clinician will administer 360 mg gentamicin IM. The gentamicin injections will be given as 2 injections of 4 mL each, one in each gluteus maximus. The time of injection will be recorded

4. *Pharmacokinetics data:*

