Subjects will be assigned post-injection blood draw at either 30 minutes, 45 minutes or 60 minutes after the gentamicin injection in a sequential fashion, meaning that participant #1 will have a 30 minute draw, #2 a 45 minute and #3 at 60 minute. This one green top tube of blood will be tested for gentamicin concentration as part of Objective 2 and Creatinine.

5. *Counseling:*

The study clinician will counsel the subject to avoid sexual activity, and most specifically performing oral sex, deep kissing, and oral-anal sex until they return for the TOC visit.

Test of Cure Visit

Subjects will return to the PHSKC STD Clinic to meet with the study clinician 4-7 days (+/- 1 day) after their enrollment visit. The study coordinator will call the subject the day prior to the visit as a reminder. At the TOC visit:

1. *Diagnostics:*

The study clinician will obtain a pharyngeal culture for *N. gonorrhoeae* and a blood draw for a follow-up creatinine. (Specimen processing per above). If the culture is positive for *N. gonorrhoeae*, the subject will be called to return for standard of care treatment – Ceftriaxone 250mg IM plus Azithromycin 1g orally once.

2. *Behavior and Symptom screen:*

The study clinician will administer a standardized symptom screening form (see Appendix F) to assess for gentamicin side effects and tolerability. The form will also ask about sexual activity, including kissing, in the time period between treatment and TOC.

Retention Plan

The study coordinator will attempt to schedule the TOC visit at 4 days after the enrollment visit so that if the subject fails to show to that visit, there are still opportunities to reschedule the TOC visit. Additionally, although the subject will be compensated for their time in the study, they will not receive compensation until they return for the TOC visit. This is an incentive for them to keep their follow-up visit.

Data Sources and Data Management

PHSKC STD Clinic Medical Record: We will use gonorrhea test results that occurred prior to enrollment visit from the STD clinic medical record for inclusion criteria. This data will be extracted by chart review during the enrollment visit using subject name and DOB as identifiers. The information will then be entered using a subject ID in the study database. We will also use demographic and sexual behavior data from the medical record.

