Related: The AE is clearly related to the study procedures.

AEs are identified at the TOC visit using the symptom screen, and with Creatinine monitoring.

SAEs and specific procedure-associated AEs are reported to the Medical Monitor within 24 hours. In addition, all AEs are reported according to the University of Washington AE reporting guidelines.

MANAGEMENT OF RISKS TO SUBJECTS

Expected AEs

Expected AEs associated with gentamicin include:

- Pain at injection site
- Bruising at injection site

AE Management

- Warm compresses as needed
- Tylenol as needed

DATA ANALYSIS PLANS

The Medical Monitor will conduct interim analyses after we have primary outcome results for 10 and 25 subjects. (Enrollment will pause until analyses can be conducted). Stopping rules include the primary end point (i.e. pharyngeal cure rate), and adverse events. If after 10 and 25 subjects, the cure rate is $\leq 44\%$ (99% CI 17% – 74%; i.e. 11 persons of 25 persons with a positive culture on treatment date fail treatment), we will stop the study. We chose these numbers using the O'Brien-Fleming method of alpha spending for multiple analyses, assuming an alpha of 0.003 for the first analysis and an alpha of 0.049 for the final analysis. Using the 99% CI obtained with 11/25 treatment failures, the upper bound is less than 75%. (Our hypothesis is that gentamicin alone will be 80% effective for pharyngeal gonorrhea, with the goal to use it in combination with a second agent). Alternatively, if at interim analysis more than 20% of subjects (99% CI 20% - 46%) have a greater than 40% increase in their creatinine from baseline, we will halt the study.

Data Analysis

The proposed study aims to evaluate the efficacy of a single intramuscular (IM) dose of 360 mg of gentamicin in the treatment of pharyngeal gonorrhea. Secondary objectives include evaluating the renal safety and tolerability of 360mg of gentamicin, *documenting peak serum gentamicin levels by subject weight*, and estimating the ideal pharmacodynamic criterion using a combination of peak gentamicin concentration levels compared to MIC and treatment outcomes. *In exploratory analyses*, we will attempt to determine whether gentamicin-monotherapy induces antimicrobial resistance among treatment failures. The specific aims are:

- 1) Determine the proportion of persons whose pharyngeal gonococcal infections are cured with a single dose of 360mg gentamicin intramuscularly alone.

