- 2) Evaluate the renal safety and tolerability of 360mg IM of gentamicin.
- 3) Document mean peak gentamicin levels following 360mg IM of gentamicin stratified by weight.
- 4) Estimate the best pharmacodynamics criterion (i.e. peak/MIC ratio) for pharyngeal gonorrhea treated with gentamicin *using individual* and mean peak gentamicin levels and NG isolate MIC.
- 5) Among treatment failures, *conduct exploratory analyses* comparing pre- and post-treatment MIC for evidence of induced resistance.

Analyses

The primary endpoint is the pharyngeal cure rate – that is, the proportion of subjects who return for TOC who clear their infections as evidenced by a negative culture 4-7 (+/-1) days after treatment. The cure rate will be calculated as the number of cured subjects divided by the total number of subjects who received treatment and returned for follow-up testing in a modified an intention to treat (mITT) analysis. We will also calculate the 95% CI for this proportion.

$$\text{Cure rate} = \frac{\text{number of subjects with negative pharyngeal culture at TOC}}{\text{number of subjects with + throat test at enrollment \& received gentamicin}}$$

Persons who test negative for NG at their enrollment visit (i.e. infection cleared between initial clinical screening test and enrollment) will be excluded from analysis. Treatment failure will be defined as a positive culture 4-7 (+/-1) days after treatment.

For our second objective, we will obtain pre- and post-treatment serum creatinine. An elevation of >40% will be considered significant. We will evaluate subject's tolerability (Obj. 2) using a standardized symptom questionnaire (see Appendix F) conducted at the TOC visit. The symptoms questioned will include, but not be limited to, rash, tinnitus, decreased hearing, nausea, vomiting, diarrhea, headaches, and decreased appetite. There will also be a section for free response.

Our third objective is to document the pharmacokinetics of 360mg of IM gentamicin by weight. We will obtain serum gentamicin levels at 30, 45 and 60minutes post dosing based on previous studies that estimated that IM gentamicin peaks between 30-60 minutes post-dose.

We will stratify the results by time post-dose, as well as by subject weight in kilograms (categorized).

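### The renal safety aim is analysed only by whether creatinine rose more than 40%; no planned analysis estimates the average paired change, although both values are collected

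*Combined protocol and SAP*

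**What the plan says.** Specific aim 2 is to "Evaluate the renal safety and tolerability of 360mg IM of gentamicin". For this aim the Analyses part of the Data Analysis section says that creatinine will be measured before and after treatment, and then gives one criterion: "An elevation of >40% will be considered significant". The Statistical Analysis Plan in the opening summary says "We plan to obtain pre-treatment and post-treatment Creatinine" and applies the same 40% cut. The halting rules, both under Data Analysis Plans in the safety monitoring section and at the end of Data Analysis, also count subjects above +40%.

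Two values exist for each returning subject. For the first, Diagnostics and Baseline Clinical Data says "This blood draw will occur with the PK blood draw 30, 45, or 60 minutes after dosing". The second is taken at the Test of Cure Visit: "a blood draw for a follow-up creatinine".

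No section plans a mean, median, geometric mean ratio, paired test or interval for the creatinine change. The Analyses text gives no interval for the proportion above +40% either; the only renal intervals in the document support halting thresholds. For the peak/MIC ratio, by contrast, the plan specifies a log transform, a geometric mean and an anticipated 95% CI.

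**The concern.** A yes/no cut at +40% treats a subject whose creatinine rose 35% the same as one whose creatinine did not move. In a cohort this small the count above the cut says little about a moderate shift in the whole group. A low count could be reported as evidence of renal safety while the average had risen, and no prespecified analysis would show it. If the mean change were calculated only after the data were seen, the choice of summary would be post hoc.

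**Working it through.** **Inputs from the document.** Planned enrollment: "Sample Size: 60 persons", one cohort, no control arm. Evaluable subjects: about 50, because the peak/MIC calculation uses 40 cures at an 80% cure rate (40/0.80 = 50). Cut: a ratio above 1.4. Interim look: 25 subjects.

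**Assumptions, not in the document.** The log of the TOC/enrollment creatinine ratio is normal with SD 0.10 to 0.25. There are 50 complete pairs. The test is two-sided at 0.05. The illustrative true mean rise is 10% (ratio 1.10).

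**The plan's own figures first.** The opening summary supports 20% (5 of 25) with a 95% CI of 7–40%. The exact interval is 6.8–40.7%, so this reproduces up to rounding. The peak/MIC interval is 3 ± 1.96 × 1/√40 = 2.69 to 3.31, which matches the stated 2.7–3.3. The plan states no figure for mean creatinine change.

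**What the cut shows.** The share above +40% is 1 − Φ[(ln 1.4 − ln m)/SD], with m the true mean ratio. At SD 0.15:
- no rise: (0.3365 − 0)/0.15 = 2.243, share 1.24%, or 0.62 of 50;
- 10% rise: (0.3365 − 0.0953)/0.15 = 1.608, share 5.39%, or 2.7 of 50.

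**What the paired mean shows.** The 95% CI half-width on the log scale is t × SD/√50 with t = 2.01 on 49 degrees of freedom. At SD 0.15 this is 2.01 × 0.15/7.071 = 0.0426, about ±4.4% after back-transformation. Power comes from the noncentral t with noncentrality ln 1.1 × √50/SD, which is 0.0953 × 7.071/0.15 = 4.49 and gives 99%.

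| Assumed SD | Expected above +40%, no rise (of 50) | Expected above +40%, 10% rise (of 50) | 95% CI of paired mean | Power for 10% rise | Rise detectable with 80% power |
|---|---|---|---|---|---|
| 0.10 | 0.02 | 0.4 | ±2.9% | >99% | 4.1% |
| 0.15 | 0.6 | 2.7 | ±4.4% | 99% | 6.3% |
| 0.20 | 2.3 | 5.7 | ±5.8% | 91% | 8.4% |
| 0.25 | 4.5 | 8.4 | ±7.4% | 75% | 10.6% |

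**Reading the count.** At SD 0.15, two or fewer subjects above the cut has probability 98% with no rise and 49% with a 10% rise, so the count separates the two poorly. It also depends heavily on the unknown SD: no rise at SD 0.25 gives a higher expected count (4.5) than a 10% rise at SD 0.15 (2.7). Seeing 0 of 50 leaves an exact 95% upper limit of 1 − 0.025^(1/50) = 7.1%.

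**The interim rule.** Under a 10% rise, the chance of 6 or more of 25 (more than 20%) is under 0.1%, 0.2%, 5.8% and 23% across the four SDs. The chance of 8 or more of 25 (32% or more) is under 0.1%, under 0.1%, 0.5% and 4.6%. The halting rule would therefore seldom show such a shift.

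**The case against.** **The information is not lost.** A reader might infer that the trial is unable to see a moderate average rise. The document does not support that: both values are kept, and the plan does not say that nothing else will be reported. The Medical Monitor reviews renal toxicity in aggregate, and the adverse event definitions include laboratory alterations. This stands. The gap is one of specification, since none of these provisions defines a group summary.

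**The 10% target is not the plan's.** The plan defines renal harm per person, by a large individual rise. A mean can stay flat while a few subjects are harmed. This also stands: the paired mean complements the threshold and does not replace it.

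**The size depends on an assumed SD.** At SD 0.25 power for a 10% rise is 75%, below the usual 80%. A run of no rises above 40% is not the typical result under a 10% shift either: the chance of 0 of 50 is 67% at SD 0.10, 6% at 0.15 and 0.2% at 0.20. The contrast between the two summaries remains, but should be quoted over the whole range.

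**The mean change has its own weaknesses.** There is no control arm. The first sample follows the injection by 30, 45 or 60 minutes. Specimens go to the laboratory in monthly batches, and the plan does not say that a subject's two samples are assayed together. A batch offset of a few percent matters to an interval of ±3% to ±7%, but hardly to a 40% cut. These points limit interpretation. The absence of a control and the timing of the first sample apply to the >40% count as well.

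**Conclusion.** The point holds as a gap in the planned analysis of a secondary aim. Every analysis of creatinine is the >40% cut, and no average paired change is planned. With 50 pairs and an assumed log-ratio SD of 0.10–0.25, a 10% mean rise adds roughly 0.4 to 4 subjects to the expected count above the cut. The paired mean would estimate that rise to within about ±3% to ±7%, with 75% to over 99% power.

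This rests on the assumed SD, approximate normality of the log ratio and about 50 complete pairs. A reader might infer that the 40% threshold is wrong, or that the halting definition should change; nothing here supports either. Nor would a mean rise, if found, establish an effect of gentamicin.

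**What to change.** In the Analyses part of the Data Analysis section, for the second objective:

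1. Keep the proportion with a rise above 40% and report it with an exact 95% CI.
2. Add the geometric mean ratio of TOC to enrollment creatinine with a 95% CI, from the paired log values, as a complement to the threshold.
3. Define the renal analysis set as all dosed subjects with both values, including those culture-negative at enrollment. The present exclusion of those subjects belongs to the cure rate; they were still exposed to the drug.
4. State that the first sample is drawn 30–60 minutes after dosing, and reconcile this with the places that call it pre-treatment.
5. State that, without a control arm, a mean change cannot be attributed to gentamicin with certainty.

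A regression of the change on dose per kg or gentamicin level is not needed. With a fixed 360 mg dose, dose per kg is only inverse weight, and the level depends on the assigned draw time. If such a model is wanted, label it exploratory and adjust for draw time.

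Separately, the halting proportion is given as more than 20% in two places and as 32% or more in a third; those passages must be reconciled.

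The cost is a few lines of text and one paired analysis of data already collected. The small downside is one more descriptive estimate that is sensitive to assay batch and baseline timing.

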We will use study IDs to label data items that only pertain to the study – i.e. data entry form, aliquots for gentamicin level and creatinine. Specimens that are also clinical specimen, will be labeled with the patient's clinic label. Data will be obtained from the medical record and entered into the data entry form which will only be labeled with the Study ID. We will maintain a separate data base in RedCap that links the patient study ID and PHI. RedCap is 21 CFR part 11 compliant. We will destroy the link between the patient's identifying data and study ID after the study has been published or by December 31, 2021, whichever is sooner.

Laboratory Processing

Gentamicin & Creatinine levels:

Draw blood for enrollment day gentamicin level and baseline creatinine at 30, 45 or 60 minutes (timing to be pre-determined by sequential participants; i.e. participant 1 is drawn at 30 minutes, 2 at 45 minutes and 3 at 60 minutes) following administration of gentamicin 360mg IM. Use green top (sodium heparin) tube. Centrifuge and aliquot ~ 2mL into 5ml Sarstedt polypropylene tube. These will be transferred to freezer within 4 hours and frozen at -80 degrees celsius until transferred to UW RTS Lab in monthly batches. UW RTS determines peak Genatmicin levels using Enzyme Immunoassay Technique and Creatinine by Spectrophotometric technique.

N. gonorrhoeae cultures and Antimicrobial Susceptibility Testing

All gonorrhea cultures are clinical specimens. The PHSKC STD Clinic's policy is to collect specimens for *N. gonorrhoeae* culture from persons with 1) a NAAT positive test who are not yet treated (i.e. most of our subjects); 2) persons with symptoms of urethritis, or cervicitis; 3) persons who are a contact to gonorrhea, at all exposed anatomic sites; and 4) persons who need a test of cure (TOC). TOC are done for any person with a cefixime, ceftriaxone or azithromycin alert value MIC, or have pharyngeal gonorrhea treated with a non-ceftriaxone containing regimen (i.e. study subjects).

Clinical gonorrhea cultures are first sent to the PHSKC Laboratory for culture and identification, and *N. gonorrhoeae* isolates are then sent to the University of Washington's Neisseria Reference Laboratory (NRL) for antimicrobial susceptibility testing (AST) for surveillance purposes. Once a culture is identified as positive growth for gonorrhea, a report is made into the PHSKC STD Clinic medical record.

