In order to estimate the ideal PK/PD criterion, we will compare the MIC of cures to treatment failures using a stratified approach (Table 2), and we will correlate this data with individual peak gentamicin level in order to estimate the ideal pharmacodynamic (PD) criterion (Obj. 4). As these results are ratios and may have a skewed distribution, we will log transform them and calculate a geometric mean. We anticipate that the vast majority of isolates will have a gentamicin MIC ≤ 8 $\mu\text{g/mL}$, and that most subjects' peak concentration will be between 16-27 $\mu\text{g/mL}$ giving a ratio of 2-4. Variations in subjects' weight or the gentamicin MICs might alter those predictions. Assuming an 80% cure rate ($n=40$), and a mean ratio of 3, with a standard deviation of 1, we anticipate a 95% CI of the peak/MIC ratio of 2.7 – 3.3, suggesting that our sample size is adequate to calculate this ratio.

For persons who fail treatment we will also compare the pre- and post-treatment gentamicin MIC to estimate whether single dose gentamicin therapy can “induce” resistance (Obj. 5) in an exploratory analysis. We will consider an increase in the MIC by two doubling-dilutions (i.e. from MIC of 2 to 8 $\mu\text{g/mL}$, or 8 to 32 $\mu\text{g/mL}$) to represent induced resistance, and we will calculate the proportion of isolates among those that fail treatment that demonstrate induced resistance following receipt of gentamicin. Should we see a signal for induced resistance, we plan to apply for additional funding to conduct whole genome sequencing to look for genetic determinants of resistance.

Table 2: Proposed Description of Primary Study Findings

GENTAMICIN MIC ($\mu\text{g/mL}$)	Cure (N=XX)	Treatment Failures (N=XX)	Gentamicin Serum Level (Mean, Range)	Peak/MIC Ratio (Mean, Range)
≤ 1				
2				
4				
8				
16				
32				
≥ 64				

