APPENDIX E

Study ID: _____

The Gent Study – Enrollment Data Entry Form

Date: _____ Age: _____ Race/ethnicity: _____

Current Gender: Male Female Trans MTF Trans FTM NB/GQ

Sex Assigned at Birth: Male Female

Gender of Sex Partners: Male Female Trans MTF Trans FTM NB/GQ

HIV Status: Positive Negative Number of oral sex partners <2 months: ____

Date of last oral sex exposure: _____

Anatomic Sites of Gonorrhea Infection and Date and Test Type:

Pharynx: Test Date: _____ **NAAT** Yes No **Culture** Yes No

NAAT Type: _____

Rectum: Test Date: _____ **NAAT** Yes No **Culture** Yes No

NAAT Type: _____

Urethra: Test Date: _____ **NAAT** Yes No **Culture** Yes No

NAAT Type: _____

Cervix/Vagina: Test Date: _____ **NAAT** Yes No **Culture** Yes No

NAAT Type: _____

Height: _____ cm

Weight: _____ kg

Medical History:

Current Medications (and doses): _____

Date & Time of Administration of Gentamicin: _____

Date & Time of Blood Draw for Gent PK and Cr: _____

Immediate reactions (if any):

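### Aim 4 treats a single level drawn at 30, 45 or 60 minutes as the individual peak, so the peak/MIC ratio sits at or below its true value and varies with the draw slot

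*Combined protocol and SAP*

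**What the plan says.** **Sampling.** Study Procedures, item 4 (Pharmacokinetics data), gives each subject one draw: "Subjects will be assigned post-injection blood draw at either 30 minutes, 45 minutes or 60 minutes after the gentamicin injection in a sequential fashion", so that "participant #1 will have a 30 minute draw, #2 a 45 minute and #3 at 60 minute". Item 2 of the same section takes the baseline creatinine from this draw "to avoid obtaining blood from the subject more than once". There is therefore one concentration per subject.

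**Label.** Laboratory Processing already calls the result a peak: "UW RTS determines peak Genatmicin levels using Enzyme Immunoassay Technique". The Analyses part of Data Analysis justifies the three times by earlier studies that put the peak of intramuscular gentamicin somewhere between 30 and 60 minutes. That is a range, not a single time.

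**Use.** Aim 4 seeks the best peak/MIC ratio from individual and mean peak levels. The analysis text says "we will correlate this data with individual peak gentamicin level in order to estimate the ideal pharmacodynamic (PD) criterion (Obj. 4". Table 2 has one row per MIC value, one serum-level column and one peak/MIC column. Neither place mentions draw time.

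**Draw time elsewhere.** Directly after the third-objective paragraph the plan says "We will stratify the results by time post-dose, as well as by subject weight in kilograms (categorized". The actual times are recorded: Appendix E has a field for the time of the injection and another for "Date & Time of Blood Draw for Gent PK and Cr".

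**The concern.** Aim 4 is meant to yield a numerical criterion, a peak/MIC ratio associated with cure. Its numerator is a concentration at a time fixed by enrolment order. Subjects whose level peaked before or after their slot are recorded below their peak. Two subjects with identical exposure and the same MIC can have different ratios because one was drawn at 30 minutes and the other at 45.

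The plan calls the sample size adequate because the ratio's 95% interval would be 2.7 to 3.3. That interval describes sampling error around whatever was measured. Slot noise would enter the observed standard deviation, but a downward shift of the whole interval would not show. The study could then report, with apparent precision, a peak-based criterion that it did not measure.

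**Working it through.** **Inputs from the plan (Data Analysis, Analyses):** mean ratio 3, SD 1, n = 40 at an 80% cure rate, stated interval 2.7 to 3.3, peak between 30 and 60 minutes. One draw per subject, three rotating slots. The documents give no half-life and no expected difference between slots; values for these below are assumptions.

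**1. The plan's own figure.** 3 ± 1.96 × 1/√40 = 3 ± 0.31, or 2.69 to 3.31 (t-based 2.68 to 3.32). The stated interval is reproduced and is not in dispute.

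**2. Direction.** For any subject, C(draw time) ≤ maximum of C(t), assay error aside. Dividing both sides by the same MIC keeps the inequality. No outside data are needed.

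**3. Size, simple assumption.** Suppose one slot hits the common peak and the other two read a fraction d lower. With equal slots, mean ratio = 3 × (1 − 2d/3), with the half-width held at 0.31:

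| d (assumed) | Mean ratio reads | Interval |
|---|---|---|
| 5% | 2.90 | 2.59 to 3.21 |
| 10% | 2.80 | 2.49 to 3.11 |
| 20% | 2.60 | 2.29 to 2.91 |

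The plan intends a geometric mean. On that scale the reading is 3 × (1 − d)^(2/3), or 2.90, 2.80 and 2.59, which is nearly the same.

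**4. Size, pharmacokinetic assumption.** One compartment with first-order absorption: C(t) ∝ exp(−ke·t) − exp(−ka·t), ke = ln 2/half-life, and ka solved from Tmax = ln(ka/ke)/(ka − ke). Tmax is spread evenly over the plan's 30 to 60 minutes. Measured level as a percentage of the true peak:

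| Half-life (assumed) | 30 min | 45 min | 60 min | Average | 3.0 reads | Worst case |
|---|---|---|---|---|---|---|
| 1.5 h | 93.6 | 98.6 | 95.5 | 95.9 | 2.876 | 84.0 |
| 2 h | 94.1 | 98.8 | 96.3 | 96.4 | 2.891 | 85.1 |
| 3 h | 94.9 | 99.0 | 97.2 | 97.1 | 2.912 | 86.8 |
| 4 h | 95.5 | 99.2 | 97.8 | 97.5 | 2.925 | 88.0 |

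The average shortfall is about 3% to 4%, and at worst 16% for one subject. If Tmax were spread over 15 to 90 minutes, beyond the plan's range, with half-life 2 to 3 h, the average would be 91.8% to 93.0% of peak, a 3.0 would read 2.753 to 2.791, and the worst case would be about 67%.

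**5. Noise.** In the 20% case, two thirds of ratios near 3 are lowered by 0.6. Slot SD = 0.6 × √(1/3 × 2/3) = 0.28. Added to SD 1, the total is √(1 + 0.08) = 1.04, so a standardised cure-versus-failure difference shrinks by about 4%. In the 10% case slot SD is 0.14 and the shrinkage is about 1%.

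**6. Cure versus failure.** Reading n = 40 as the cures, 40/0.8 = 50 evaluable subjects and 10 failures. In the 20% case the slot adds a standard error of 0.28 × √(1/40 + 1/10) = 0.10 to the difference in means, against 1 × √(1/40 + 1/10) = 0.35 from ordinary variation. With slots of 17, 17 and 16 and outcome unrelated to slot, the hypergeometric chance that six or more of the 10 failures share one slot is about 0.061 + 0.061 + 0.044 = 17%.

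**The case against.** The strongest reply is that the plan already recognises draw time: it stratifies by time post-dose, spreads the slots across the expected peak window, and rotates them so that they should be unrelated to MIC and outcome. Within that window the average shortfall is probably a few percent, Aim 4 is secondary, and Table 2 is a proposed layout whose level column speaks of serum level rather than peak.

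Much of this stands, and it rules out several stronger readings that a reader might infer:

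- *That the Aim 3 mean levels are biased by pooling over slots.* The time stratification follows the Aim 3 text, and no section plans a pooled mean for that aim.
- *That slot confounds cure with failure.* Assignment by enrolment order gives no reason for a systematic link. Chance imbalance is possible (step 6), but its contribution is small beside ordinary variation.
- *That one subject's shift from 3.0 to 2.4 can be set against the 2.7 to 3.3 interval.* That interval is for a mean. The like-for-like shift in the 20% case is 0.4; for one subject the scale is the SD of 1.
- *That the highest of the three slot means should be reported as the mean peak.* This selects on noise. With three equal true means of about 20 subjects each, the expected excess is 0.846 standard errors. If 16 to 27 µg/mL spans ±1 to ±2 SD (an assumption; CV 26% to 13%), that is 0.846 × CV/√20, about 4.8% to 2.4%, comparable to the shortfall being corrected.

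The reply does not answer the central point. Stratifying levels by time shows differences between slot means; it does not turn one sample into an individual peak, and it is not carried into Objective 4 or Table 2, where the value is used as a peak.

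**Conclusion.** The point holds for Aim 4 and is worth correcting before analysis. The design facts and the direction are firm: the ratio as planned is at or below true peak/MIC and includes slot-related noise, and the 2.7 to 3.3 interval does not reveal the downward shift.

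The size is not established. It is about 3% to 4% on average if all peaks lie in the plan's window and half-life is 1.5 to 4 hours. It is larger if slots differ more: 3.0 reads 2.8 or 2.6 when two slots are 10% or 20% low. The 20% case is an upper scenario that the documents do not support as likely. Slot mainly adds modest noise and a downward shift. The primary cure rate and the stopping rules do not depend on this value.

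**What to change.** 1. In the Objective 4 text and Table 2, call the value the concentration at the sampled time (30 to 60 min), and call the ratio concentration/MIC.
2. In Aim 4, adjust log concentration for the recorded minutes from injection to draw, standardising to a reference time named in advance, or include draw time as a covariate in the cure-versus-failure comparison. The plan already log-transforms the ratios.
3. Show the ratio by slot alongside Table 2. With 40 cures split into about 13 per slot, the half-width grows from 0.31 to 1.96/√13.3 = 0.54, so this is for display rather than separate inference.
4. State the limit. Adjustment brings levels to a common time and does not recover individual peaks. The unadjusted ratio is a lower bound on peak/MIC for each subject, assay error aside. The standardised ratio is a lower bound only on average, because it assumes the same curve shape for everyone.

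The cost is analysis wording and one or two degrees of freedom for draw time. No extra blood, visit or data item is needed, since both clock times are already on Appendix E.
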